12.2 Informed Consent	

1 ABSTRACT

Title:

A single-center, open, single-arm clinical study on the application of ursodeoxycholic acid for the prevention of novel coronavirus infections

Planned research time:

Expected to enroll healthy volunteers for 3 weeks and follow up for 8 weeks

Purpose of the study:

1) Primary research objectives

Evaluation of the efficacy and safety of ursodeoxycholic acid in blocking the transmission of infectious novel coronaviruses in a population of medical workers

2) Secondary Research Objectives

Exploring the evaluation of conversion to severe disease in people infected with novel coronavirus

Exploring the evaluation of the persistence and reduction of symptoms in people infected with novel coronavirus

Exploring the evaluation of antibody profiles in healthy volunteer populations Observing the safety of ursodeoxycholic acid drugs

Evaluating the changes of S protein-specific T/B cell immunity before and after BF.7 infection after immunization with Wuhan Strain vaccine.

Study population:

Healthy volunteers for this study were from medical workers (doctors, nurses, medical technicians, administrative logistics, medical students) who were not infected with novel coronavirus

Planned enrollment (sample size):

The study is expected to enroll 130 healthy volunteers

Study Design Overview:

This study is a single-center, open-ended, single-arm clinical study

Inclusion Criteria:

Healthy volunteers suitable for enrollment in this study must meet all of the following criteria:

- 1) Age 18-65 years old
- 2) No restriction on gender
- 3) Medical-related personnel (working hours >20 hours per week) serving during the COVID-19 outbreak, including physicians, nurses, medical technicians, administrators, and medical students
- 4) COVID-19 nucleic acid test negative within 48 hours
- 5) Sign the informed consent form

Exclusion Criteria:

Anyone who meets any of the following criteria shall not be selected for this study:

- 1) Exhibit COVID-19 symptoms, including fever, muscle pain, headache, cough, sore throat, and loss of smell and taste
- 2) Previous infection with novel coronavirus within 6 months
- 3) Previous (past 30 days), current or planned (during the study period) use of immunomodulatory-related drugs
- 4) Those with allergy or intolerance to ursodeoxycholic acid, gallbladder or bile duct disease, severe liver failure, or liver function impairment
- 5) Pregnancy and lactation
- 6) Use of drugs with which ursodeoxycholic acid is contraindicated
- 7) Other reported health conditions that make participation in the study not in the best interest of the individual

Shedding and exit criteria

- 1) Healthy volunteers request to withdraw from the study on their own
- 2) Female healthy volunteers planning to become pregnant or pregnant during the trial
- 3) Missed visits due to various reasons
- 4) In the judgment of the investigator, treatment should be discontinued from this protocol

Rejection Criteria:

- 1) Poor compliance with the requirements of the study and failure to follow the study plan
- 2) Those who received prophylactic drugs other than this drug during the trial

Research drug delivery protocols:

Drug name (specification formulation): ursodeoxycholic acid capsules.

Mode of administration/regimen: 250 mg/capsule, 2 capsules per day, for 4 weeks.

Duration of follow-up visits:

Dosing period:

Healthy volunteers took ursodeoxycholic acid capsules daily for 4 weeks from the date of enrollment

Follow-up period:

Healthy volunteers will be followed up once a week for a total of 8 weeks in case of new coronavirus infection.

Research Indicators:

1) Primary research indicators

Prevalence of novel coronavirus infection in healthy volunteers receiving 4 weeks of continuous ursodeoxycholic acid plus conventional protection during the study period.

- 2) Secondary Research Metrics
 - 1) The proportion of people infected with novel coronavirus who turned severe.
- 2) the number of days that symptoms of a novel coronavirus infection such as fever, sore throat, headache, and muscle aches persisted in the population infected with novel coronavirus, and the number of days that the nucleic acid/antigen turned negative.
 - 3) The rate of positive serological antibodies in the population of healthy volunteers.
 - 4) The incidence of adverse events.

5) The difference of T/B lymphocyte specific response to Wuhan Strain and BF.7 Strain in different volunteers.

Safety evaluation:

Observe and record any adverse events that occur in healthy volunteers during the clinical study, including abnormal clinical symptoms and vital signs, abnormalities in laboratory tests, record the characteristics of clinical manifestations, severity, time of occurrence, duration, management and prognosis, and determine their correlation with the trial drug/treatment regimen, and evaluate safety according to NCI CTCAE version 5.0 standards

Statistical Methods:

SAS 9.4 software was used for statistical analysis of the data in this study, with continuous variables described by mean \pm stan dard deviation (Mean \pm SD) or median, maximum, minimum, and interquartile range (Median, Max, Min, IQR) and categorical variables described by rate or percentage. Comparisons of measurement data were performed by t-test/ANOVA or nonparametric test; comparisons of count data were performed by $\chi 2$ test or Fisher's exact probability test. If not otherwise specified, all tests were performed as two-sided tests with a test level of α =0.05.

2 Research Background

Researchers at the University of Cambridge, UK, and other institutions have found that ursodeoxycholic acid (UDCA) is able to turn off the ACE2 receptor, thereby blocking viral entry into human cells, and since the SARS-CoV from 2003 to the SARS-CoV-2 spectrum in 2019 utilizes ACE2 as the primary invasion receptor, even if subsequent SARS-CoV-2s continue to show new small variants, the drug maintains its effect. The study was published in Nature on December 5, 2022, entitled "FXR inhibition may protect from SARS-CoV-2 infection by reducing ACE2" [1]. Ursodeoxycholic acid (UDCA) was found to downregulate angiotensin-converting enzyme 2 (ACE2) expression by inhibiting the transcription factor FXR, thereby shutting down the entry of neocoronavirus into human cells. Since the drug acts on the host cell and not on the virus itself, it may be able to prevent current neo-coronavirus infections and should also be able to prevent future neo-coronavirus new mutants, as well as infections by other coronaviruses that utilize ACE2. Currently, China is in a period of high prevalence of neo-coronavirus infections, and there is an urgent need for clinical studies on prophylactic drugs

3 Research objectives

The purpose of this study is to evaluate whether ursodeoxycholic acid is an effective prophylactic agent against novel coronavirus (SARS-CoV-2) infection in medical personnel

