5.3 Off study criteria

Volunteers withdrew from the study for any of the following reasons.

- 1) A healthy volunteer's own request to withdraw from the study.
- 2) planned pregnancy or pregnancy during the trial in female healthy volunteers.
- 3) Loss of visit for various reasons.
- 4) The investigator's judgment should discontinue treatment in this protocol.

Healthy volunteers may withdraw their informed consent if they do not wish to continue to participate in the study. If a healthy volunteer decides to withdraw from the study, the investigator must be notified in a timely manner. The reason for withdrawal from the study should be documented, including the date and reason for withdrawal from the study.

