5.4 Rejection Criteria

Volunteers were required to be excluded from the study for the following conditions

- 1) Those who are poorly compliant with the requirements of the study and fail to follow the study plan.
- 2) Those who receive prophylactic medications other than this drug during the trial.

6 Drug delivery measures

Drug Name (Specification Formulation).

Ursodeoxycholic acid capsule, 250mg/capsule.

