11.2 Statistical analysis set

Full analysis dataset (FAS): is a dataset determined according to the Intention-To-Treat (ITT) principle and includes all enrolled healthy volunteers who have used the study drug at least once and have at least one analyzable efficacy indicator, and validity analysis is based on the FAS.

Protocol-compliant dataset (PPS): a subset of the overall FAS, including healthy volunteers who did not show significant protocol deviations in the full analysis set, used as an adjunct to the validity analysis.

Safety data set (SS): all healthy volunteers enrolled who received the trial drug and had at least one post-dose safety evaluation data, safety analysis was based on SS.

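### An investigator's decision to stop treatment, or poor compliance, takes a volunteer out of the study with no later infection testing, which conflicts with the ITT-based primary analysis set

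*Protocol*

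**What the plan says.** Protocol section 5.3 opens its list with "Volunteers withdrew from the study for any of the following reasons". Among the reasons are "Loss of visit for various reasons" and "The investigator's judgment should discontinue treatment in this protocol". The abstract gives a parallel list of shedding and exit criteria, with "Missed visits due to various reasons" in place of the former and "In the judgment of the investigator, treatment should be discontinued from this protocol" in place of the latter. Section 5.4 adds volunteers to be excluded from the study, among them "Those who are poorly compliant with the requirements of the study and fail to follow the study plan".

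The abstract sets 4 weeks of dosing, and the abstract and section 4 set weekly infection follow-up over 8 weeks. Sections 7.2 and 7.3 provide weekly testing and weekly telephone calls about adverse events. None of these sections says that tests or calls go on for a volunteer who has met an exit or rejection criterion.

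Section 11.2 bases the efficacy analysis on an FAS determined by the intention-to-treat principle. It "includes all enrolled healthy volunteers who have used the study drug at least once" and who have at least one analysable efficacy indicator. Section 8.1 defines the primary endpoint as the proportion of the study population infected during the study. Section 11.3 reports it as a number and percentage with a Clopper-Pearson 95% interval. Neither section says how incomplete follow-up is counted.

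**The concern.** An intention-to-treat analysis needs outcomes for everyone in the set, whether or not they keep taking the drug. Here a decision about treatment also ends participation, and with it the search for infection. A volunteer taken off the drug in week 2 with one negative test meets the FAS definition, but an infection in week 5 would not be looked for.

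The study has a single arm, so no concurrent control loses outcomes in the same way. Any shortfall in detected infections goes straight into the comparison with the 35% historical rate on which section 11.1 rests. An analysis plan can set how such volunteers are counted, but it cannot recover infections that were never sought. This is therefore a matter of study conduct and belongs in the protocol.

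**Working it through.** **1. The plan's own figure.** Inputs from section 11.1: p0 = 0.35, p1 = 0.20, two-sided α = 0.05, power 90%, one-sample z-test with continuity correction.

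- n = [(1.960·√(0.35·0.65) + 1.282·√(0.20·0.80)) / 0.15]² = [(0.9348 + 0.5126)/0.15]² = 93.1.
- With continuity correction: (93.1/4)·(1 + √(1 + 2/(93.1·0.15)))² = 99.7, rounded up to 100.
- With 20% dropout: 100/0.80 = 125. The position quotas sum to 20+30+20+20+20+20 = 130.

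The stated 100 reproduces, and 130 covers the dropout allowance. The sample size is not in question.

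**2. Success rule (assumption).** Section 11.3 states no decision rule. I take success to mean that the exact two-sided 95% upper limit lies below 35%. With n = 130, 34 infections give an upper limit of 34.6% and 35 give 35.4%, so success means 34 or fewer. With no early exits and a true rate of 35%, P(X ≤ 34) = 2.0%.

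**3. Leavers kept in the denominator and counted as uninfected after exit.** Assume constant hazards of infection and of exit over the follow-up window:

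- infection hazard λ = −ln(0.65) = 0.4308;
- exit hazard μ = −ln(1 − L), where L is the share that these rules would remove in the absence of infection;
- observed rate = λ/(λ+μ)·[1 − exp(−(λ+μ))], where exp(−(λ+μ)) = 0.65·(1 − L).

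| L | μ | Observed rate when the truth is 35% | P(X ≤ 34), n = 130 |
|---|---|---|---|
| 0 | 0 | 35.0% | 2.0% |
| 5% | 0.0513 | 34.2% | 3.1% |
| 10% | 0.1054 | 33.3% | 4.8% |
| 20% | 0.2231 | 31.6% | 10.5% |

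For L = 20%: 0.4308/0.6539·(1 − 0.52) = 0.316.

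**4. Sensitivity to the timing of exits.** Let f be the share of a leaver's infection risk that falls before exit. Then observed rate = 0.35·[(1 − L) + L·f]. With L = 20%:

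- f = 0.75 gives 33.3% and a 5% chance of apparent benefit;
- f = 0.5 gives 31.5% and 11%;
- f = 0 gives 28.0% and 36%.

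The document gives no value for f. Under this counting the rate never rises, but the amount by which it falls depends heavily on f.

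**5. Leavers dropped from the denominator.** Let leavers have r times the infection risk of stayers, with 20% leaving and a true overall rate of 35%. The stayers' rate is 0.35/(0.8 + 0.2·r):

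- r = 0.5 gives 38.9%;
- r = 1 gives 35.0%;
- r = 1.5 gives 31.8%;
- r = 2 gives 29.2%.

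Under this counting the direction is not fixed.

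**The case against.** **Follow-up does not end with treatment as a general rule.** Dosing lasts 4 weeks and infection follow-up 8, so volunteers who stay in are tested after their last capsule. A reader might infer that anyone who stops the drug leaves the study. The text does not go so far: the treatment criterion covers the investigator's judgment. A volunteer who stops unprompted is caught only by withdrawing or through the compliance rule in 5.4. This stands and narrows the point.

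**One missed visit.** A reader might also infer that a single missed weekly visit removes a volunteer. Only the literal wording of the abstract supports that. Section 5.3 can be read as loss to follow-up, and section 11.1 uses shedding to mean dropout. The two wordings need reconciling, but no attrition estimate should be built on the stricter one.

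**Direction.** A flat statement that the primary rate is understated would go beyond the document. Section 11.2 does not define an analysable efficacy indicator, no rule covers incomplete follow-up, and adding a 20% allowance to 100 cases may mean that dropouts were to be treated as non-evaluable. The direction is conditional.

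**Size.** The 20% allowance covers all causes, including voluntary withdrawal and true loss, which no rewording recovers. Charging all of it to these rules overstates their effect.

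**Illness and missed tests.** One could suppose that ill volunteers miss tests and so escape detection. Section 7.3 allows testing at any time on symptoms and accepts a positive self-test antigen, so a symptomatic volunteer still in the study need not wait for the weekly test. The calculation does not use this argument.

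The objection leaves the core untouched: the listed exits end participation, and nothing continues testing after them.

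**Conclusion.** The point holds in a limited form. Sections 5.3 and 5.4 and the abstract tie leaving the study to an investigator's decision on treatment and to poor compliance, without infection testing afterwards. That is inconsistent with an FAS said to follow intention to treat and with a primary result that is a crude percentage.

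Understatement follows if leavers remain in the denominator as uninfected. That is the natural reading of sections 8.1, 11.2 and 11.3 taken together, but none of them states it. How many volunteers these rules would remove, and when, is not in the document, so the size is unknown. On the constant-hazard assumption and the assumed success rule, the false-success chance of 2.0% becomes 3.1% or 4.8% with 5% or 10% removed. The 10.5% at 20% is an upper illustration as regards the share removed. Exits earlier than the model assumes would raise each figure, and later exits would lower it. The change is cheap and worth making.

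**What to change.** In sections 5.3 and 5.4 and the abstract, separate stopping the drug from leaving the study. State that a volunteer who is taken off the drug or complies poorly continues the weekly testing and telephone contact already scheduled, to the end of follow-up, unless consent is withdrawn. Reconcile "Missed visits due to various reasons" in the abstract with "Loss of visit for various reasons" in 5.3, so that only volunteers who cannot be reached count as lost to follow-up. State, in the protocol or the analysis plan, how volunteers with incomplete follow-up enter the primary percentage.

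This leaves untouched when or why treatment is stopped. It costs a few lines of text and a few more weekly tests and calls for volunteers who are off the drug.

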3.1 Primary research objectives

Evaluation of the effectiveness and safety of ursodeoxycholic acid in blocking the transmission of infectious novel coronaviruses in adult populations

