7.1 Screening Period

- Baseline Collection
 - 1) Basic demographic information such as age and sex.
 - 2) Type of neo-coronavirus vaccination and number of vaccinations received.
 - 3) novel coronavirus infection status of family members/personnel living with them.
 - 4) Personnel positions: e.g., physicians, nurses, medical technology, administrative logistics, medical students, etc.

- 5) Working department.
- 6) underlying disease status: e.g. hypertension, diabetes, cardiovascular disease, etc.
- 7) Combined medication use and drug allergy history.
- Routine Inspection:
 - 1) Vital signs (heart rate, respiration, body temperature, etc.
- Retention of serum samples:
- 1) 5mL of blood was collected from healthy volunteers, of which 2mL of whole blood was directly frozen and the rest was extracted from the serum for freezing and storage.
 - 2) Biological sample processing and storage.

Blood samples will be collected according to the follow-up plan, and the processing and storage will be carried out by the Biosample Bank of the Hospital of Blood Diseases, Chinese Academy of Medical Sciences. It will be managed in strict accordance with biosafety law, regulations on human genetic resources management and other relevant regulations.

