7.2 Dosing period (4 weeks)

- 1) weekly nucleic acid testing (in lieu of nucleic acid results if positive for self-test antigens)
 - 2) Weekly telephone follow-up for adverse events.
- 3) 5mL of blood is collected from healthy volunteers at the end of dosing or in case of infection during the period, of which 2mL of whole blood is directly frozen and the rest is extracted from the serum for freezing.

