7.3 Follow-up period (8 weeks)

1) If a healthy volunteer develops novel coronavirus symptoms during the follow-up period, the volunteer's symptoms will be scored and recorded according to Table 1.

Table 1: New crown symptom assessment form

Symptoms	Rating				
	Slight =1	Medium =2	Serious =3	Score	
Abdominal					
pain					
fatigue					
Cough					
Shortness of					
breath					
Diarrhea					
Muscle pain					
Headaches					
Taste and					
smell disorder					

Other		
Total Score		

- 1) Weekly telephone follow-up of AE status of healthy volunteers.
- 2) Detection of antibodies before and after drug administration.
- 3) Weekly monitoring of nucleic acid/antigen status of new crowns in healthy volunteers during the study period, and testing for nucleic acid at any time during the study period when volunteers develop symptoms of novel coronavirus (in case of positive self-test antigen, this can be substituted for nucleic acid results)./
- 4) Blood will be collected for freezing and storage in case of infection and out of the group.

Table 2: Table of observation items during the visit

	Baseline period	Detection frequency	In case of infection
Demographic Information	√		
Nucleic acid testing	√	Weekly	√
Vital signs	√		
AE Telephone follow-up AE	√	Weekly	
Blood collection for freezing and storage	√	Week 4 and 8	

[figure not shown]

Figure 1: Research flow chart

[figure not shown]

Figure 2: Flow chart of the visit

8 Research indicators

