8.3 Safety indicators

Observation and recording of various adverse events during administration of ursodeoxycholic acid in healthy volunteers

9 Adverse events and serious adverse events

All adverse events, including abnormal clinical symptoms and vital signs, and abnormalities in laboratory tests from the date of signing the informed consent to the last visit were recorded, and the characteristics of clinical manifestations, severity, time of occurrence, duration, management and prognosis were recorded, and their correlation with the trial drug/therapeutic regimen was determined.

Adverse events were graded and recorded with reference to NCI CTCAE 5.0

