9.1 Adverse Events

9.1.1 Definition of Adverse Events

Adverse event: An adverse medical event that occurs after a healthy volunteer participates in a clinical study, not necessarily related to the study treatment, and includes any

new event that occurs or worsens in severity and frequency compared to the baseline situation, including abnormal results of laboratory tests, physical examinations, etc. Adverse events include Severe adverse event (SAE), Adverse event (AE), and abnormal laboratory results.

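### Adverse events are defined to include laboratory and vital-sign abnormalities, but the visible schedule has no safety laboratory test and no vital signs after baseline, so a low or zero count of such events is not evidence of safety.

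*Protocol*

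**What the plan says.** **Scope of safety.** Section 3.1 of the Protocol gives as primary objective "Evaluation of the effectiveness and safety of ursodeoxycholic acid", and the abstract's primary objective also names safety. The abstract's safety evaluation covers events "including abnormal clinical symptoms and vital signs, abnormalities in laboratory tests", evaluated by CTCAE 5.0. The opening paragraph of section 9, which follows section 8.3, repeats this scope: "abnormalities in laboratory tests from the date of signing the informed consent to the last visit were recorded". Section 9.1.1 defines an event as something new, or worse in severity or frequency, relative to the baseline state, and adds: "Adverse events include Severe adverse event (SAE), Adverse event (AE), and abnormal laboratory results".

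**Schedule.** Under routine inspection at screening, section 7.1 lists one item: "Vital signs (heart rate, respiration, body temperature, etc". Table 2 ticks vital signs in the baseline column and leaves the other two columns empty. In the dosing period, events are sought by "Weekly telephone follow-up for adverse events" (section 7.2), and in the follow-up period by "Weekly telephone follow-up of AE status of healthy volunteers" (section 7.3). The laboratory work listed is "weekly nucleic acid testing (in lieu of nucleic acid results if positive for self-test antigens" and its continuation in follow-up, antibody detection before and after dosing, and blood drawn for freezing and storage.

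**Analysis.** Section 11.2 admits to the safety set any dosed volunteer with at least one post-dose safety evaluation. Section 11.3, item 4, has adverse events and serious adverse events recorded, described and judged for relevance.

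**The concern.** An event defined as a change from baseline in a measured quantity can be found systematically only if that quantity is measured at baseline and again later. The Protocol names two such quantities, laboratory values and vital signs, and the visible schedule plans a second measurement of neither. For safety laboratory values it does not plan a first.

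What is at stake is the reading of the safety result. A report that follows the Protocol's own definition would present laboratory and vital-sign abnormalities as part of what was evaluated. If few or none were listed, the natural reading would be that volunteers were checked and found normal. In fact most may never have been checked. Because safety shares the primary objective with effectiveness, that reading would bear on one of the trial's main conclusions.

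**Working it through.** The Protocol gives no figure on this point, so the check sets the definition against the schedule.

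| Component | Within the adverse-event scope (abstract; section 9 opening; 9.1.1) | Scheduled at baseline (7.1; Table 2) | Scheduled after baseline (7.2; 7.3; Table 2) |
|---|---|---|---|
| Symptoms and other events a volunteer can report | Yes | Yes (telephone row ticked) | Yes, weekly call |
| Vital signs | Yes | Yes | None listed |
| Safety laboratory values | Yes | None listed | None listed |

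1. **Vital signs.** One scheduled set per volunteer, before dosing. A comparison with baseline needs at least two, so the schedule yields no planned comparison.

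2. **Safety laboratory values.** No scheduled value before dosing and none after, so again no planned comparison, and not even a baseline.

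3. **The laboratory work that is listed.** Nucleic acid or antigen testing serves the primary infection indicator (section 8.1). Antibody detection serves a secondary indicator (section 8.2, item 3). The blood draws are described as being for freezing and storage, and no safety assay is named for them. None of these provides a safety laboratory value.

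4. **What the telephone call can find.** It can find what a volunteer knows: symptoms, a self-measured temperature, or a result from care obtained elsewhere. Who has such a result depends on individual circumstances, so the number of volunteers measured is not fixed by the design and not known in advance.

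5. **The denominator.** Section 11.2 asks for one post-dose safety evaluation, and on its face a single telephone call satisfies this. Volunteers never measured after baseline would then be counted in the safety set. Dividing laboratory or vital-sign events by the size of that set would treat people who were not measured as people who were measured and normal.

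It follows that the weekly calls support a statement about reported events. The visible design does not support one about laboratory or vital-sign safety.

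**The case against.** **A definition is not a promise to measure.** The abstract and section 9 can be read as saying what is recorded if it comes to light. This stands in part: it means that these events are not systematically sought, not that they can never be found. It does not close the gap, because section 9.1.1 ties an event to a comparison with baseline and the abstract presents laboratory and vital-sign abnormalities as part of the safety evaluation.

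**Safety does not drive the main result.** Observing safety is also listed as a secondary objective (section 3.2), adverse-event incidence is a secondary indicator (section 8.2), and the only primary indicator is infection (section 8.1). Section 8.3 describes the safety indicator without naming laboratory values. All this is correct and limits the weight of the point: no test or decision rule depends on laboratory safety. The primary objective nevertheless names safety, so a safety conclusion will be drawn.

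**Content not shown.** Figures 1 and 2 are missing from the text available, and the annexes show no content. A measurement listed only there cannot be excluded. If one exists, Table 2 still has to be brought into line with it.

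**Stronger readings.** A reader might infer that no laboratory test is scheduled at all. That is wrong, since nucleic acid and antibody tests are. A reader might infer that laboratory and vital-sign events must come out at zero. That does not follow, since the calls can pick up self-measured or outside results, the volunteers are medical workers, and section 11.1 expects about 20% to be infected. A reader might attach an exact upper confidence limit to a zero count. Section 11.3, item 4, plans no interval for safety, and without a known number measured such a limit would have no meaning. Finally, a reader might suppose that the stored serum could supply the missing values. The Protocol does not show that its volume, its suitability or the consent would allow this.

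**Conclusion.** The point holds as a mismatch between definition and schedule. Laboratory and vital-sign abnormalities are within the stated safety evaluation. The visible text schedules no safety laboratory test at any time and no vital signs after baseline. Such events would be found unsystematically, over an unknown number of volunteers measured, and a low or zero count would not be evidence of safety.

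Its size cannot be given as a rate, because the Protocol fixes no number measured. In terms of design, the schedule plans no post-baseline measurement of either kind for any of the 130 planned volunteers. The infection result and the description of reported events are unaffected.

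The conclusion assumes that sections 7.1 to 7.3 and Table 2 are the complete schedule and that the missing flow charts add no safety measurement. It takes no position on whether laboratory monitoring is clinically needed. The liver-function exclusion in section 5.2 does not settle that question.

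**What to change.** Reconcile the adverse-event definition (abstract, section 9 opening, section 9.1.1) with the visit schedule (sections 7.1 to 7.3, Table 2). If safety measurements are in fact made, list what is measured and when in Table 2. If they are not, make at least these changes:

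- In the abstract and section 8.3, limit the safety indicator, and any conclusion drawn from it, to events reported by volunteers.
- State in the Protocol and in the report that laboratory and vital-sign safety was not systematically assessed.
- In section 11.3, item 4, provide that any laboratory or vital-sign event that comes to light is reported over the volunteers who had that quantity measured after dosing, with that number shown, and not over the whole safety set.

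The minimum version costs wording, plus a record of who was actually measured. It needs no new visit, sample or assay. The downside is a narrower safety claim: the trial could speak to reported events only.
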